### 3. TECHNICAL SUMMARY REPORT

Name of Sponsor/Company The Romark Institute for Medical Research	Individual Study Table Referring to Part of the Dossier: Volume:	(For National Authority Use Only):		
Name of Finished Product: Nitazoxanide 300 mg Tablets	Page:			
Name of Active Ingredient: Nitazoxanide				
Title Of Study: A Phase 3, Randomized, Double-Blind, Placebo Controlled Trial to Evaluate the Efficacy and Safety of Nitazoxanide in the Treatment of Colds Due to Enterovirus/Rhinovirus Infection				
Investigators: Multicenter				
Studied period: August 2018 – April 2019	Phase of development: 3			
Objectives:				

The primary objective of the study is to evaluate the effect of nitazoxanide (NTZ) administered orally 600 mg b.i.d. for 5 days in reducing the duration of symptoms of colds due to Enterovirus/Rhinovirus (EV/RV) infection compared to placebo during 21 days of follow-up based upon the FLU-PRO® patient-reported outcome instrument. A key secondary efficacy objective is to evaluate the effect of NTZ compared to placebo on time to return to ability to perform all normal activities.
 
Another secondary efficacy objective is to evaluate the effect of NTZ compared to placebo on the proportion of subjects experiencing one or more complications of colds due to EV/RV infection including pneumonia, otitis media, bronchitis, sinusitis, exacerbations of asthma or COPD, worsening of pre-existing health conditions, secondary infections requiring systemic antibiotic use, hospitalization due to cold or complications of the cold, and death due to cold or complications of the cold.
 
Exploratory efficacy objectives include evaluating the effect of treatment with NTZ on the time to response for each FLU-PRO symptom; time to response for each FLU-PRO domain; time to return to usual health; changes in viral titers from Baseline to each of Days 2, 3 and 7; time to symptom response, time to ability to perform all normal activities, and proportions experiencing complications for all subjects treated (ITT population); time to symptom response for subjects infected with individual non-EV/RV viruses; and time to symptom response for subjects who received the first dose of study medication 0-24, >24-≤36, or >36 hours from symptom onset. A final exploratory objective is to evaluate the impact of symptom relief medication use on time to symptom response, time to return to ability to perform all normal activities, and proportions experiencing complications of colds for placebo-treated subjects.
 
Other important objectives include evaluation of the safety of NTZ by analysis of adverse events and evaluation of relationships between pharmacokinetics and clinical or virologic responses.
				
Number of Subjects: 530 subjects with laboratory-confirmed EV/RV infection and complete data for analysis purposes, estimated to require at least 600 (up to maximum of 700) with colds due to laboratory-confirmed EV/RV infection				
Study Design:				
Multicenter, randomized, double-blind, placebo controlled trial to evaluate efficacy and safety of NTZ in the treatment of colds due to EV/RV infection				
Population: Males and females ≥12 years of age with EV/RV infection				
Study dose and mode of administration:				
Group 1 (NTZ): Two NTZ 300 mg tablets orally twice daily (b.i.d.) with food for 5 days				
Group 2 (Placebo): Two placebo tablets orally b.i.d. with food for 5 days				

**Statistical methods:**

Let  $S_0(t)$  and  $S_1(t)$  be the underlying survival functions regarding the time to Symptom Response for placebo and NTZ, respectively. The null and alternative hypotheses for the primary objective are defined as follows:

$$H_0: S_1(t) = S_0(t)$$

$$H_A: S_1(t) \neq S_0(t)$$

The time to Symptom Response for subjects with laboratory-confirmed EV/RV infection (ITI population) will be compared using a Gehan-Wilcoxon test at the  $\alpha=0.05$  level (two-tailed) stratified by (1) time from onset of illness to time of first dose of study medication (0-24, >24-≤36, or >36 hours from onset), (2) pre-enrollment use of symptom relief medication, and (3) presence of underlying lung condition including asthma, COPD, or past or present history of smoking.

## 6. LIST OF ABBREVIATIONS

Abbreviation	Definition
ALT	Alanine aminotransferase
AST	Aspartate aminotransferase
b.i.d.	bis in die (twice daily)
BUN	Blood urea nitrogen
COPD	Chronic obstructive pulmonary disease
CRF	Case report form
CSR	Clinical study report
EDC	Electronic data capture
EV/RV	Enterovirus/Rhinovirus
FDA	U.S. Food and Drug Administration
FLU-PRO	inFLUenza Patient-Reported Outcomes
GGT	Gamma-glutamyltransferase
HDL	High-density lipoprotein
hMPV	Human metapneumovirus
ITT	Intent to treat
ITI	Intent to treat infected
LDL	Low-density lipoprotein
MedDRA	Medical Dictionary for Regulatory Activities
NTZ	Nitazoxanide
RSV	Respiratory syncytial virus
RT-PCR	Real time polymerase chain reaction
SAP	Statistical analysis plan
SOC	System Organ Class
T	Tizoxanide
TEAE	Treatment-emergent adverse event
TG	Tizoxanide Glucuronide
WHODrug	World Health Organization Drug dictionary

## 7. INTRODUCTION

The purpose of this statistical analysis plan (SAP) is to describe the planned analyses and data displays to be included in the Clinical Study Report (CSR) for Protocol RM08-3005.

All decisions regarding final analysis as defined in this SAP will be made prior to database lock and unblinding of the study data. Further information can be found in the protocol.

The SAP is based on:

- Protocol RM08-3005, Final Version 1.3, November 29, 2018
- International Conference on Harmonisation Guidelines E4 and E9; and
- Discussions with the U.S. Food and Drug Administration (FDA).

This document will describe analysis populations and detail methodology for deriving variables, handling missing data, and analyzing efficacy and safety data.

The SAP may be revised or amended to reflect the requirements of protocol amendments or regulatory requests, but must be finalized, approved and placed on file before the database is locked. Deviations from the SAP will be noted in the CSR.

## 8. STUDY DESCRIPTION

### 8.1. Study Objectives

The primary objective of this study is to evaluate the effect of NTZ administered orally 600 mg b.i.d. for 5 days in reducing the duration of symptoms of colds due to EV/RV infection compared to that of a placebo during 21 days of follow-up based upon the FLU-PRO® patient-reported outcome instrument.

A key secondary efficacy objective is to evaluate the effect of NTZ compared to placebo on time to return to ability to perform all normal activities.

Another secondary efficacy objective is to evaluate the effect of NTZ compared to placebo on the proportion of subjects experiencing one or more complications of colds due to EV/RV infection including pneumonia, otitis media, bronchitis, sinusitis, exacerbations of asthma or COPD, worsening of pre-existing health conditions, secondary infections requiring systemic antibiotic use, hospitalization due to cold or complications of the cold, and death due to cold or complications of the cold.

Exploratory efficacy objectives include evaluating the effect of treatment with NTZ on the time to response for each FLU-PRO symptom; time to response for each FLU-PRO domain; time to return to usual health; changes in viral titers from Baseline to each of Days 2, 3 and 7; time to symptom response for all subjects treated (ITT population); time to symptom response for subjects infected with individual non-EV/RV viruses; and time to symptom response for subjects who received the first dose of study medication 0-24, >24-≤36, or >36 hours from symptom onset. A final exploratory objective is to evaluate the impact of symptom relief medication use on time to symptom response, time to return to ability to perform all normal activities, and proportions experiencing complications of colds for placebo-treated subjects.

Other important objectives include evaluation of the safety of NTZ by analysis of adverse events and evaluation of relationships between pharmacokinetics and clinical or virologic responses.

## 8.2. Study Design

The study will be a multicenter, randomized, double-blind trial to evaluate the efficacy of NTZ compared to placebo in treating colds due to EV/RV infection. Subjects will be selected according to the inclusion and exclusion criteria listed in the protocol.

Immediately after completion of informed consent, screening, and enrollment in the study, two Baseline nasopharyngeal swabs will be collected for RT-PCR. Blood and urine samples will be collected for laboratory safety tests. Subjects will receive instruction on completing their electronic diaries, recording concomitant medications and attending follow-up visits.

Subjects will be randomized 1:1 to one of the following groups:

- Group 1 (NTZ): Two NTZ 300 mg tablets b.i.d. for 5 days
- Group 2 (Placebo): Two placebo tablets b.i.d. for 5 days

Randomization will be stratified by (1) time from onset of illness to time of first dose of study medication (0-24, >24-≤36, or >36 hours from onset), (2) pre-enrollment use of symptom relief medication, and (3) presence of underlying lung condition including asthma, COPD, or past or present history of smoking.

Study medication will be taken in the morning and evening with food. The first dose will be taken with food in the physician's office under the observation of the Principal Investigator or a member of the Investigator's staff. The second dose will be taken by the patient as close as possible to 12 hours after the first dose.

A nurse or other study personnel will visit each subject (or the subject will return to the clinic) on study Days 2 and 3 to collect two nasopharyngeal swabs, to review patient diaries, and to review symptoms and screen for complications of colds. A blood sample for pharmacokinetics will also be collected prior to the first dose of study medication on study Day 3. These Day 2 and 3 visits will occur at approximately the same time of day that the subject took his/her first dose of study medication (roughly 24 and 48 hours post-first dose). The nasopharyngeal swabs will be used to evaluate quantitative changes in viral shedding. The blood sample will be used to evaluate relationships between pharmacokinetics and virologic or clinical response. Study sites or subjects may opt out of the Day 2 and Day 3 visits due to site staffing, patient availability or other practical considerations or preferences; nevertheless, at least 75% of subjects enrolled in the trial are expected to complete the Day 2 and Day 3 visits and related procedures (for viral kinetics and pharmacokinetics).

A study physician, nurse or other site personnel will make daily telephone calls to subjects for the first five days of dosing to review symptoms and screen for complications of colds. [Note: In lieu of a telephone call, this information may be obtained during the Day 2 or 3 office or home visits (see the preceding paragraph).]

Subjects will return to the clinic on Days 7 and 22 for post-treatment follow-up, including two nasopharyngeal swabs, drug accountability, and reporting of adverse events and complications of cold. Blood and urine samples for laboratory safety tests will be collected

[figure not shown]
at Day 7. Subjects will maintain the electronic patient diaries through study Day 21. Any visits that do not occur on the prescribed date, or within 1 day of that date in the case of the Day 7 visit or within 3 days after in the case of the Day 22 visit will be recorded as protocol deviations.

A central laboratory will be used for laboratory safety tests and virology testing. Laboratory safety tests will include hemoglobin, hematocrit, complete blood count (total and differential), platelet count, random blood sugar, total cholesterol, HDL, LDL, triglycerides, albumin, AST, ALT, GGT, alkaline phosphatase, bilirubin (total/direct), BUN, creatinine, sodium, potassium, chloride and routine urinalysis (glucose, protein and blood). Virology testing will include RT-PCR assay to identify influenza A (non-specific as to subtype); influenza A H1, H1N1 (2009), and H3 subtypes; influenza B; respiratory syncytial virus A and B (RSV); parainfluenza 1, 2, 3 and 4; human metapneumovirus (hMPV); adenovirus; human EV/RV; coronavirus NL63, HKU1, 229E and OC43; human bocavirus; *Chlamydophila pneumoniae*; *Legionella pneumophila*; and *Mycoplasma pneumoniae*. (Baseline and Day 7 nasopharyngeal swabs), and quantitation of EV/RV by quantitative PCR (Baseline and Days 2, 3 and 7 nasopharyngeal swabs). Follow-up samples (Days 2, 3 and 7) collected from subjects who do not test positive for EV/RV at Baseline, Day 2 or Day 3 will not be analyzed for quantitative virus titer.

This study is expected to run from August 2018 through April 2019.

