3. STUDY DESIGN

The study will be a multicenter, randomized, double-blind trial to evaluate the efficacy of NTZ compared to placebo in treating colds due to EV/RV infection.

Subjects will be randomized 1:1 to one of the following groups:

- Group 1 (NTZ): Two NTZ 300 mg tablets b.i.d. for 5 days
- Group 2 (Placebo): Two placebo tablets b.i.d. for 5 days

Enrollment and the primary efficacy analysis will be stratified by (1) time from onset of illness to study enrollment (0-24, >24-≤36, or >36 hours from onset), (2) pre-enrollment use of symptom relief medication, and (3) presence of underlying lung condition including asthma, COPD, or past or present history of smoking.

This study is expected to run from August 2018 through April 2019.

Rationale for important issues in the study design is described below:

- *Choice of NTZ dose and duration of treatment.* The dose of NTZ used for this clinical trial (600 mg b.i.d. for 5 days) was associated with a reduction of the duration of symptoms and time to ability to perform all normal activities in subjects with EV/RV infection in a previous trial of NTZ for the treatment of influenza (Study RM08-3002). In clinical trials involving 2,886 subjects, adverse events reported by subjects receiving 600 mg NTZ b.i.d. for 5 days were similar to those of subjects receiving the placebo, with the exception of a higher rate of diarrhea (8.1% compared to 5.8% for the placebo). Studies of NTZ at higher doses have shown dose-dependent increases in the frequency of reported diarrhea and other gastrointestinal side effects, therefore no higher dose is planned for this study.
- *Choice of control groups.* A placebo control is appropriate for the study due to lack of any approved active control.
- *Choice of patient population.* The population to be studied includes adults and adolescents at least 12 years of age with EV/RV infection. This is a population similar to those selected for studies RM08-3001, RM08-3002, RM08-3003 and RM08-3004 of the NTZ 300 mg extended release tablets in more than 3,000 subjects with influenza-like illness. No safety concerns have been identified from these clinical trials.

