5.2. Baseline (day 1, same day as screening evaluation)

At baseline, the following procedures will be carried out:

1. Collection of two nasopharyngeal swabs (one from each nostril) using nylon flocked dry swabs (Copan Diagnostics) for RT-PCR and culture.
2. Collection of blood sample for laboratory safety tests.
3. Collection of a urine sample for routine urinalysis (glucose, protein and blood).
4. Review and recording of any concomitant medications.
5. Provision of an electronic diary to subject via his/her own smartphone or a provisioned device, and subject completion of baseline electronic diary under supervision and instruction of study site personnel, including the Practice Diary, FLU-PRO Questionnaire, Activity Diary, and Study Drug Intake and Temperature Diary.
6. Randomization and dispensing of study medication (medication assigned in sequential order).

7. Administration of the first dose of study medication with food (< 1 hour after food intake) under observation of Investigator or a member of Investigator's staff, and entry in Study Drug Intake and Temperature Diary.
8. Instruct subject regarding:
 - a. *Administration of study medication.* Subjects will be instructed to take the study medication (two tablets) twice daily with food (< 1 hour after food intake, preferably a high-fat meal but at a minimum a cereal bar). The subject should take his/her second dose as close as possible to 12 hours after the first dose. Then he/she will take the study medication every 12 hours for the remaining 4 days.
 - b. *Completion of subject diary.* Subjects will be instructed on completion of the electronic diary.
 - c. *Use of birth control.* Female subjects of childbearing potential, if sexually active, will be instructed to continue an acceptable method of birth control for the duration of the study and for 1 month post-treatment. Acceptable methods of birth control include a double barrier method, oral birth control pills, an IUD, or medroxyprogesterone acetate administered intramuscularly.
 - d. *Follow-up visits:* Subjects will be instructed to return to the clinic for follow-up on Day 7 and Day 22.
 - e. *Seeking emergency care or contacting the study physician or nurse:* Subjects must be informed to seek emergency medical care or contact the study physician or nurse if they develop any of the following symptoms listed below during the full 22-day study and follow-up period.

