6. RANDOMIZATION

An independent third party (██████████) will prepare a master randomization list and maintain the masking of the study. Randomization will be performed using permuted block randomization. Subjects who qualify for the study will be assigned to treatment using centralized randomization procedures stratified by time from onset of illness to study enrollment, presence of underlying chronic lung condition (asthma, COPD, history of smoking) and pre-enrollment use of symptom-relief medication. The treatment numbers will appear on the bottles containing the masked study medication. The randomization list will be masked to study participants including Sponsor, Investigators, study monitors, subjects and laboratory personnel. Unmasking for any individual subject will occur only if necessitated by emergency and knowledge of the medication being taken will influence the medical management of the subject. Furthermore, if the event warrants submission of an IND Safety Report, then the subject will be unmasked for completion of the report.

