8.4.1. Efficacy Analyses

Efficacy analyses will be based on a population consisting of all subjects that received at least one dose of study drug and had laboratory-documented EV/RV infection (infected intent-to-treat or ITTI population). Laboratory-documented EV/RV infection is defined by identification of EV/RV in nasopharyngeal secretions by RT-PCR at baseline, Day 2 or Day 3. For time to event analyses a test of significance (as described in the following) will be performed with descriptive statistics provided including the use of Kaplan-Meier figures.

There will be one primary efficacy analysis:

- Time to Symptom Response for the NTZ treatment group will be compared to that of the placebo treatment group using a stratified Gehan-Wilcoxon test ($\alpha = 0.05$) where stratification will follow that used for randomization. Subjects without a Symptom Response being recorded will be treated as censored as of their last diary without a documented Symptom Response.

If the primary analysis is significant at the 0.05 level, a key secondary efficacy analysis will be formally evaluated at the 0.05 level as follows:

- Time to Ability to Perform All Normal Activities for the two treatment groups will be compared using a stratified Gehan-Wilcoxon test ($\alpha = 0.05$) where stratification will follow that used for randomization. Subjects without an Ability to Perform All Normal Activities response being recorded will be treated as censored as of their last diary without a documented Ability to Perform All Normal Activities response.

If both the primary analysis and the key secondary efficacy analysis are significant at the 0.05 level, another secondary efficacy analysis will be formally evaluated at the 0.05 level as follows:

- Proportions of subjects experiencing one or more complications of colds due to EV/RV infection will be compared between the treatment groups using a Cochran-Mantel-Haenszel test stratified by the randomization strata ($\alpha = 0.05$).

Exploratory analyses will be performed as follows:

- For each of the 32 individual FLU-PRO symptoms, Time to Individual Symptom Response for the NTZ and placebo treatment groups will be compared using the Gehan-Wilcoxon test.
- For each of the 6 FLU-PRO domains, Time to FLU-PRO Domain Response for the NTZ and placebo treatment groups will be compared using the Gehan-Wilcoxon test.

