1.2	14Jun2019	[REDACTED]	
Update to:
 
 
1. Add exploratory analysis of time to symptom response for subjects who received the first dose of study medication 0-24, >24-≤36, or >36 hours from symptom onset (Sections 3, 8.1, 11.5.8, 11.5.9, 11.5.10, Appendix 2);
 
2. Add exploratory analysis of time to symptom response by symptom relief medication use (placebo-treated subjects only), time to ability to perform normal activities by symptom relief medication use (placebo-treated subjects only), and proportions experiencing complications of colds by symptom relief medication use (Sections 3, 8.1, 11.6.2, 11.6.3, 11.6.4, Appendix 2);
 
3. Add the “No pathogen detected” subgroup as a possible analysis population for time to symptom response for subjects without EV/RV infection (Sections 3, 8.1, 11.5.7);
 
4. Clarify number of subjects required (Section 3);
 
5. Clarify calculation of “time from symptom onset” to mean the time in hours between the time of first dose of study medication and the patient-reported time of symptom onset (Sections 3, 8.2, 11.2, 11.4.1, 11.5.2, 11.5.3);
 
6. Remove oral temperature and qualifying symptoms from the Baseline Disease Characteristics table and listing due to lack of relevance and explicit documentation in the database, respectively (Sections 10.1.4, 10.2);
 
7. Update cumulative distribution parameters for selection of maximum symptom response criteria from 75%-90% to 90%-95% (Section 11.2.1);
 
8. Clarify maximum symptom response criteria procedure including improvement of example case (Section 11.2.1);
 
9. Clarify impact of symptom relief medication use on Time to FLU-PRO Domain Response analysis (Section 11.5.2);
 
10. Clarify that ePlex RPP RT-PCR and quantitative PCR tests should be considered for analysis of proportions of subjects with detectable virus (Section 11.5.5);
 

Ver	Date	Revision Author	Comments

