#### **11.2.2. Analysis of the Primary Efficacy Parameter**

The primary efficacy parameter, time to Symptom Response, will be derived as follows:

Event: Time of Symptom Response – time of the first dose

Censored: Time of last symptom assessment – time of the first dose

If Symptom Response is achieved at the time of the first symptom assessment diary record, the subject will be excluded from the analysis.

If Symptom Response is not achieved prior to a subject’s last available diary assessment, but the criteria are met at the last available diary assessment with no evidence of symptom relief medication intake during that diary period, time of Symptom Response will be considered to have occurred at the start of the last daily diary period.

Time to Symptom Response for the NTZ treatment group will be compared to that of the placebo treatment group using a Gehan-Wilcoxon test stratified by (1) time from onset of illness to time of first dose of study medication (0-24, >24-≤36, or >36 hours from onset), (2) pre-enrollment use of symptom relief medication, and (3) presence of underlying lung condition including asthma, COPD, or past or present history of smoking. The comparison will be graphically depicted using Kaplan-Meier curves.

Analysis Population(s): ITTI

Derived Variables: Event: Time of Symptom Response – time of first dose

Censored: Time of last symptom assessment – time of first dose

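### The SAP stratifies the primary and key secondary tests by onset to first dose, while the protocol binds them to the randomization strata, which use onset to enrollment

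*SAP*

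**What the plan says.** **Protocol (version 1.3).** Section 3 sets one onset factor for both allocation and analysis: "Enrollment and the primary efficacy analysis will be stratified by (1) time from onset of illness to study enrollment", with bands of 0-24, >24 to 36, and >36 hours. Section 6 repeats it for allocation: "centralized randomization procedures stratified by time from onset of illness to study enrollment". Section 8.4.1 specifies the primary and the key secondary Gehan-Wilcoxon tests, each time "where stratification will follow that used for randomization".

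**SAP (version 1.4).** Section 11.2.2 specifies the primary comparison "using a Gehan-Wilcoxon test stratified by (1) time from onset of illness to time of first dose of study medication". Sections 3 and 11.2 describe the primary test in the same way, and section 11.4.1 uses the same factor for the key secondary test. Section 8.2, describing the design, says "Randomization will be stratified by (1) time from onset of illness to time of first dose of study medication". The hour bands and the other two factors (pre-enrollment symptom relief medication and underlying lung condition) match the protocol.

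**History.** The SAP revision table lists the first-dose definition among the version 1.2 changes (14 June 2019) and presents it as a clarification: the interval is said "to mean the time in hours between the time of first dose of study medication and the patient-reported time of symptom onset". SAP section 7 says the plan is based on protocol version 1.3, which still says enrollment.

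**Order of events.** In protocol section 5.2, step 6 begins "Randomization and dispensing of study medication (medication assigned in sequential order". Step 7 is the first dose, taken with food under observation.

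**The concern.** The two current documents define the onset stratum by different clock times. Under the protocol, the strata of the primary and key secondary tests are those in which subjects were allocated. Under the SAP, they depend on a time fixed only after allocation. SAP 8.2 hides the difference by attributing the later time to randomization itself.

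The main thing at stake is clarity about which test is the primary one. The two stratifications can give different p-values on the same data, and the primary p-value decides whether the key secondary test is formally evaluated (SAP 11.4). If the result fell close to 0.05, a reader could not tell from the documents which version governs. A lesser matter is that some subjects would be compared within a stratum other than the one in which they were block-randomized.

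**Working it through.** **1. Texts side by side**

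| Item | Protocol | SAP |
|---|---|---|
| Onset factor at randomization | to enrollment (3, 6) | to first dose (8.2) |
| Onset factor, primary test | to enrollment (3); same as randomization (8.4.1) | to first dose (3, 11.2, 11.2.2) |
| Onset factor, key secondary test | same as randomization (8.4.1) | to first dose (11.4.1) |
| Exploratory time-to-event tests | no stratification stated (8.4.1) | to first dose (e.g. 11.5.1-11.5.3) |

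An actual dose time at step 7 is not known at step 6, so the SAP 8.2 entry cannot describe how allocation was done. The first two rows of SAP entries and the key secondary row conflict with the protocol. The exploratory row breaks no protocol commitment.

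**2. How many subjects change stratum**

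The point rests on no sample-size figure from the plan; the 600-700 infected subjects serve only as a denominator. The inflation behind that denominator reproduces: 530 / (1 - 0.12) = 602.3, rounded up to 603, against the stated 600; and 600 × 0.88 = 528, close to 530.

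Inputs: enrollment no more than 40 h after onset (protocol 4.1) and cut-points at 24 h and 36 h. Two inputs are not in the documents and are assumed: onset-to-enrollment times uniform over 0-40 h, and the delay from enrollment to dose.

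- Fixed lag of L hours for everyone. Those within L hours below either cut-point move, so the fraction is 2L/40. L = 1, 2, 3 gives 5%, 10%, 15%. The extremes in counts are 0.05 × 600 = 30 and 0.15 × 700 = 105.
- Delay uniform from 0 to D hours, so the mean lag is D/2. The fraction is 2 × (D/2)/40 = D/40. D = 1, 2, 4 gives 2.5%, 5%, 10%; at 600 subjects that is 15, 30, 60.

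The smallest band is affected most. The >36 h group is 4/40 = 10% by enrollment and (4 + L)/40 by first dose: 12.5% at L = 1 and 15% at L = 2.

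**3. Effect on the test**

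A simulation compared the two stratifications on the same data: 600 subjects, 12 strata (3 × 2 × 2), permuted blocks of 4 within the enrollment strata, and delay uniform up to D and independent of arm. Event times were exponential and grouped by day, with a placebo median of 146.5 h (protocol Table 5) varying modestly with the strata, 12% random dropout and censoring at 504 h. Block size, event-time shape and effect size are assumptions.

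| D | Type I error: enrollment / first dose | Power, median 35 h shorter: enrollment / first dose |
|---|---|---|
| 1 h | 0.049 / 0.048 | 0.743 / 0.733 |
| 2 h | 0.0475 / 0.047 | 0.705 / 0.713 |
| 4 h | 0.0525 / 0.0535 | 0.715 / 0.710 |

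There were 2,000 runs per type I error entry and 600 per power entry. The standard error of one entry is √(0.05 × 0.95 / 2000) = 0.005 for type I error and about √(0.72 × 0.28 / 600) = 0.018 for power. The differences are smaller than these and go in both directions. The power values illustrate one assumed effect and are not a check of the plan's 90%, whose curves are in a figure not available here.

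**The case against.** **First-dose time has a rationale.** The endpoint clock starts at first dose, the protocol's case for early enrollment concerns when treatment begins, and SAP 11.5.10-11.5.12 define subgroups by dosing time. This stands as a reason the sponsor could give. The SAP does not give it, and it does not remove the conflict with protocol 8.4.1.

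**The change was recorded and made blind.** The revision table lists it openly, and SAP section 7 requires decisions before lock and unblinding. This also stands. A reader might infer from the June 2019 date, after the planned April 2019 end of study, that the stratum was chosen with knowledge of results; nothing in the documents supports that.

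**A post-randomization stratum need not bias the test.** A reader might infer bias because the stratum is fixed after allocation. The first dose is the next listed step, at the same visit, observed and double-blind, so the delay should be short and unrelated to arm, and the drug cannot affect a time that ends when it is first taken. The simulation agrees.

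**Balance is already incomplete.** Blocks balance everyone randomized, up to 1,750, but the test uses only EV/RV-positive subjects. With 40% positive, independent of arm, subsetting alone leaves about 1 - 0.40 = 60% of the arm-imbalance variance of simple randomization, whichever onset time is used. Lost block balance is therefore a weak argument.

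**The counts depend on assumptions.** The figure of 105 needs a 3 h lag for every subject and 700 infected subjects. It counts reclassified subjects and does not measure harm.

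**Conclusion.** The inconsistency stands for the primary and key secondary tests, and the SAP 8.2 sentence is wrong as a description of randomization. The size is modest: about 2.5-10% of subjects change onset stratum for delays uniform up to 1-4 h, or 5-15% for a fixed lag of 1-3 h, both resting on an assumed uniform onset distribution over 0-40 h. Since dosing directly follows randomization at the same visit, the lower figures are more plausible. No material effect on bias, type I error or power is expected, and the sample size is unaffected.

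Two further readings go too far. SAP 8.2 might suggest that subjects were actually allocated by dosing time; protocol section 6 governs allocation and says enrollment, so this is more likely a wording carry-over from the version 1.2 edit. Nor do the exploratory tests breach the protocol, because its rule on following the randomization strata covers only the primary and key secondary time-to-event tests. Severity is low: an improvement that costs almost nothing, plus one statement to correct.

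**What to change.** - In SAP 8.2, state the randomization factor as onset to study enrollment.
- In SAP 3, 11.2, 11.2.2 and 11.4.1, define the onset stratum for the primary and key secondary tests as the stratum used at randomization, and add that variable, with its source, to Tables 6 and 7, which do not list it now.
- Keep onset to first dose for the subgroups in 11.5.10-11.5.12, and add it as a sensitivity analysis of the primary test.
- The other exploratory tests need no change to honour the protocol, though matching strata would be consistent.

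If the sponsor prefers first-dose strata for the primary test, SAP 8.2 still needs correcting, and the departure from protocol sections 3 and 8.4.1 should be declared and justified.

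The cost is essentially SAP wording plus one added variable. The documents do not say that the randomization stratum is held in the analysis data. That it can be retrieved is an inference from the use of centralized stratified randomization, and should be confirmed.
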